9 (tele)	
10 (tele)	

MAL in Follow-up Recording Form for Tele-Gaming Group:

MAL Spreadsheet (How Well Scale Only)	F/U 1	F/U 2	F/U 3	F/U 4
1. Turn on a light switch				
2. Open drawer				
3. Remove an item of clothing from a drawer				
4. Pick up phone				
5. Wipe off a kitchen counter or other surface				
6. Get out of car				
7. Open refrigerator				
8. Open a door by turning a door knob/handle				
9. Use a TV remote control				
10. Wash your hands (lathering and rinsing hands)				
11. Turning water on/off with knob/lever on faucet				
12. Dry your hands				
13. Put on your socks				
14. Take off your socks				
15. Put on your shoes				
16. Take off your shoes				
17. Get up from a chair with armrests				
18. Pull chair away from table before sitting down				
19. Pull chair toward table after sitting down				
20. Pick up a glass, bottle, drinking cup, or can				
21. Brush your teeth				
22. Use a key to unlock a door				
23. Carry an object in your hand				
24. Use a fork or spoon for eating				
25. Comb your hair				
26. Pick up a cup by a handle				
27. Button a shirt				
28. Eat half a sandwich or finger foods				
MEAN				

Limb Activation Instructions (Pebble Watch):

- If the screen is showing the time, press "select"
- Toggle down to the app "Hands On"
- Push the select button to select the Hands On app (this is the limb activation)
- When you are using the device, make sure notifications are on (see above picture for how to turn them on/off)
- IMPORTANT: In order for the notifications to work (vibrate after 10 minutes of inactivity), you must click the "back" button and you will wear it with the time visible, not the amount of movements
- However, if you prefer to have the daily count visible, that is fine too, the notifications just will not work
- Wear the watch during all of your waking hours for the duration of your participation in the study
- The watch will need to be charged every night
 - o The charger will insert into a USB on any computer and connect to the back of the watch
 - o The display on the watch will say "charging" when it's connected properly
- To reset the app, hold down the select button for a few seconds and release and everything will be set back to 0

Pebble Watch Log:

- > Please record the daily count from your watch each night before you go to bed
- > The first two days (baseline days) you will wear the watch on your unaffected arm, which will give you a goal for daily counts of your affected arm during the intervention

D .	Baseline	Baseline						
Date:						-	 	
	_	_				-	 	
Daily								
Count:								
								_
Date:		_					 	
			_			_	 	
	-							
Daily								
Count								
:								

Treatment Materials – Usual Care

Traditional Rehabilitation Protocol

Guiding Principles:

- Participants will receive the intervention on 4 visits that total 5 hours of participant/therapist contact. The 4 visits will be dispersed across the 3 weeks as evenly as possible. Ideally, the first 2 visits will occur during week 1 and the second 2 visits will be administered on weeks 2 and 3.
- The intervention will incorporate activities that are typically used in clinical settings for rehabilitation.
- The activities are designed to meet the specific needs of the participant (e.g., work to improve their body structure challenges, activity limitations, and participation goals).
- The protocol is standardized regarding activity categories, activity selection, activity intensity target level, and progression principles yet will be tailored to the participants' specific needs and goals.
- The amount of time dedicated to each activity category is specified below. It is expected that several
 trials of a given activity category may be accomplished during this time frame and it is expected that
 the number of trials may vary between participants based on their movement and endurance
 capabilities.
- For the active procedures of neuromuscular re-education, functional training, and progressive strengthening, the target for exercise intensity is 4 (somewhat hard) on the Borg CR10 Rating of Perceived Exertion Scale. Therapists should also assure that activities are conducted with high quality.
- When designing a clinical activity, therapists will select from a list of activities and grade the difficulty
 of the activity so that the participant is working at a level 4 on the Borg CR10 Rating of Exertion Scale.
 In subsequent visits, therapists should adjust the activity grade (up or down) to achieve that same
 level 4 of the Borg CR10 Scale.
- A home program will be designed for all participants on the first visit. This home program will consist of theraband strengthening exercises to be done over a 15 minute time period twice daily (total of 30 minutes each day) except on the days that they come into the laboratory for treatment. Therapists will design this program based on the participant's skill with the exercises and the appropriate level of exertion (4 on the Borg CR10 Scale). Therapists will provide written instructions on these exercise and will review and modify the exercise program, as appropriate, on subsequent clinic visits (i.e., visits 2-4).

Allocation of treatment time – The first treatment session will be 2 hours in length and subsequent treatment sessions will each be 1 hour in length.

Treatment Day 1

Activity	Evaluate for	Neuromuscular	Functional	Progressive	Establish
category	therapeutic needs	re-education	Training	Strengthening	and teach
	_				home
					program
Time	25 minutes	20 minutes	25 minutes	25 minutes	25 minutes
dedicated					
to this					
activity					

Other Treatment Days

Activity category	Review and adjust, as appropriate, home program	Neuromuscular re- education	Functional Training	Progressive Strengthening
Time dedicated to this activity	10 minutes	10 minutes	25 minutes	15 minutes

Clinical Activity Description: Neuromuscular re-education (20 minutes TD1; 10 minutes TD2-4)

Description: ICD definition: (ICD 97112)Neuromuscular re-education of movement, balance, coordination, kinesthetic sense, posture, and/or proprioception for sitting and/or standing activities Examples include: Biofeedback, PNF, manual facilitation, sensory priming.

These activities will be used to "prime" the motor responses and promote more coordinated and appropriate muscle responses during the functional training to follow.

Clinical Activity Description: Functional Training (25 minutes all treatment days)

Description: Functional training will focus around 4 categories of activities that have high relevance for functional use of the upper extremity (dexterity, interpersonal reaching, extrapersonal reaching, and overhead reaching). Each category of activities will be carried out for approximately 5 minutes, allowing another 5 minutes for switching between task categories. Participants will be seated for all activities and patients encouraged to keep their trunk against the back of the chair to promote proper posture. Assistive devices such as orthoses, taping or bandages can be used. Rest periods can be provided as much as needed.

- 1. Dexterity Participants will use the more-affected hand to engage in various manipulation tasks for approximately 5 minutes of the functional training period during each of the treatment days. The specific manipulation task selected for that day will correspond with manipulation task in need of improvement for and preferred by that participant. The task should also be moderately challenging for that individual and leads to physical exertion rating of a 4 on the Borg CR10 Scale. Examples: picking up small objects (e.g., coins, paper clips, checkers) off of a table, buttoning a shirt, flipping playing cards.
- 2. Inter-personal Space Reaching Participants will use the more-affected arm to engage in reaching and

manipulation tasks relatively close to their body (e.g., requiring less than 45 degrees of shoulder flexion). These tasks will be less likely to involve a great deal of trunk rotation and/or reaching across midline.

Examples: using a spoon to move beans from one bowl to another, moving a belt through belt loops, moving ping pong balls from one container to another.

3. Extra-personal Space Reaching – Participants will use the more-affected arm to engage in reaching and manipulation tasks relatively far away from their body (e.g., requiring between 45 and 90 degrees of shoulder flexion and approaching full extension of the elbow). These tasks will be more likely to involve trunk rotation and reaching across midline.

Examples: wiping off a counter, setting a table with eating utensils.

Overhead Reaching - Participants will use the more-affected arm to engage in reaching tasks toward a target that is held by a therapist and placed overhead (e.g., requiring greater than 90 degrees shoulder flexion and approaching full extension of the elbow).

Examples: combing hair with a brush, blow drying hair, putting a hat on/off, placing objects on a high shelf.

Clinical Activity Description: Progressive Strengthening Activities (25 minutes TD1; 15 minutes TD 2-4)

Description: Strengthening should emphasize shoulder flexion, Shoulder Abduction (with elbow extension or 90° of flexion), Shoulder External Rotation (90° elbow flexion). Each movement will be carried out according to the description taken from the GRASP exercise program with no theraband or with the color of theraband providing the level of resistance corresponding to a level 4 on the Borg CR10 Scale and that allows good quality of movement. During the session, therapists will select a number of repetitions that correspond to moderate exertion (rating of 4 on the CR10 exertion scale) and will assign that number of repetitions for the home exercise program to be carried out until the next visit. The number of repetitions will be progressed as appropriate for that patient and corresponding with strength gains while maintaining Borg level 4 and completing the program in 30 minutes.

Borg CR10 Rating of Perceived Exertion Scale

Rating	Description
0	Nothing at all
0.5	Very, very light
1	Very light
2	Fairly light
3	Moderate
4	Somewhat hard
5	Hard
6	
7	Very hard
8	

Traditional Therapy Checklist (Group 4)

Note: Bolded items are separate sheets within the treatment packet to be completed

Prior to Treatment (after pre-test)

- 1. Provide the activity monitors to participants and demonstrate use.
- 2. Instruct them to wear the activity monitors on both arms for 2 days before treatment to establish a baseline of arm use.
- 3. Make sure the participant knows to charge them overnight every night.

Treatment Day 1 (TD 1)

- 1. Turn video camera on & say participant ID, treatment day, and group
- 2. Complete Treatment Received Form
- 3. 30 minutes of evaluation of affected upper extremity function.
- 4. 20 minutes of neuromuscular re-education. Complete **Treatment Log** Day 1.
- 5. 25 minutes of functional training. Complete **Treatment Log** Day 1.
- 6. 25 minutes of progressive strengthening. Complete **Treatment Log** Day 1.
- 7. 20 minutes of teaching home program. Complete **Treatment Log** Day 1.
- 8. Ask participant about adverse events and fill out **Adverse Event Reporting Form** if need be.
- 9. Turn video camera off and add comments to Therapist Treatment Recording Log
- 10. Store the video on the encrypted hard drive under the correct group and session subfolder

Treatment Day 2 (TD 2)

- 1. Turn video camera on & say participant ID, treatment day, and group
- 2. 10 minutes of neuromuscular re-education. Complete **Treatment Log** Day 2.
- 3. 25 minutes of functional training. Complete **Treatment Log** Day 2.
- 4. 15 minutes of progressive strengthening. Complete **Treatment Log** Day 2.
- 5. 10 minutes of reviewing and updating home program. Complete **Treatment Log** Day 2.
- 6. Ask participant about adverse events and fill out **Adverse Event Reporting Form** if need be.
- 7. Turn video camera off and add comments to Therapist Treatment Recording Log
- 8. Store the video on the encrypted hard drive under the correct group and session subfolder

Treatment Day 3 (TD 3)

- 1. Turn video camera on & say participant ID, treatment day, and group
- 2. 10 minutes of neuromuscular re-education. Complete **Treatment Log** Day 3.
- 3. 25 minutes of functional training. Complete **Treatment Log** Day 3.
- 4. 15 minutes of progressive strengthening. Complete **Treatment Log** Day 3.
- 5. 10 minutes of reviewing and updating home program. Complete **Treatment Log** Day 3.
- 6. Ask participant about adverse events and fill out **Adverse Event Reporting Form** if need be.
- 7. Turn video camera off and add comments to Therapist Treatment Recording Log
- 8. Store the video on the encrypted hard drive under the correct group and session subfolder

Treatment Day 4 (TD 4)

- 1. Turn video camera on & say participant ID, treatment day, and group
- 2. 10 minutes of neuromuscular re-education. Complete Treatment Log Day 4.
- 3. 25 minutes of functional training. Complete **Treatment Log** Day 4.
- 4. 15 minutes of progressive strengthening. Complete **Treatment Log** Day 4.
- 5. 10 minutes of reviewing and updating home program. Complete **Treatment Log** Day 4.
- 6. Ask participant about adverse events and fill out **Adverse Event Reporting Form** if need be.
- 7. Turn video camera off and add comments to Therapist Treatment Recording Log
- 8. Store the video on the encrypted hard drive under the correct group and session subfolder

Video Recording Log is the same as for the Self-Gaming Group.

Usual Care Treatment Log

	TREATMENT DAY 1 (2 hours) Date:	TREATMENT DAY 2 (1 hour) Date:	TREATMENT DAY 3 (1 hour) Date:	TREAMENT DAY 4 (1 hour) Date:	
Evaluation	(30 minutes)	N/A	N/A	N/A	
Neuromuscular re- education	(20 minutes) Level: Activities completed: Intensity easy moderate hard	(10 minutes) Level: Activities completed: Intensity easy moderate hard	(10 minutes) Level: Activities completed: (10 minutes) lntensity easy moderate hard	(10 minutes) Level: Activities completed: Intensity easy moderate hard	
Functional Training (one of each: dexterous, reaching close, far, high as possible)	(25 minutes) Activities completed: 1. 2. 3. 4.	(25 minutes) Activities completed: Intensity easy moderate hard	(25 minutes) Activities completed: Intensity easy moderate hard	(25 minutes) Activities completed: Intensity easy moderate hard	
Progressive Strengthening	(25 minutes) Activities completed: Intensity easy Moderate hard	(15 minutes) Activities completed: Intensity easy moderate hard	(15 minutes) Activities completed: Intensity easy moderate hard	(15 minutes) Activities completed: Intensity easy moderate hard	
Teach, review home program (Shoulder strengthening Theraband GRASP, Pang, 2006	flexion (20 minutes) abduction extension external rotation (progress resistance of band and increasing repetitions as appropriate targeting 30 min of exercise at Borg level 4).		(10 minutes) Review and update HEP	(10 minutes) Review and update HEP	

Assessment Measures

WOLF MOTOR FUNCTION TEST DATA COLLECTION FORM

Participant ID:		Date:	Site:	
Test (check one): Pre-tre	eatment	Post-treatment_	6 month follow-up _	
Affected arm (circle one): Right	Left		
Task	Unaffect	ted Arm Time (min:sec	c) Affected Arm Time (n	nin:see)
1. Forearm to table (side)				
2. Forearm to box (side)	_			
3. Extend Elbow (side)				
4. Extend Elbow (weight)				
5. Hand to table (front)				
6. Hand to box (front)				
7. Weight to box		lbs.	lbs	
8. Reach and retrieve				
9. Lift can				
10. Lift pencil	_			
11. Lift paper clip				
12. Stack checkers				
13. Flip cards	_			
14. Grip strength	kgs,	_kgs,kgs.	kgs,kgs,	_kgs.
15. Turn key in lock				
16. Fold towel				
17 Lift basket				

Motor Activity Log (UE MAL) Score Sheet

Amount Scale How Well Scale

1.	Turn on a light with a light switch		 if no, why? (use code) Comments
2.	Open drawer		 if no, why? (use code)
3.	Remove an item of clothing from a drawer		 if no, why? (use code)
4.	Pick up phone		 if no, why? (use code)
5.	Wipe off a kitchen counter or other surface		 if no, why? (use code)
-	Get out of a car (includes only the movemen body from sitting to standing once the door is open).		 if no, why? (use code)
7.	Open refrigerator		 if no, why? (use code)
8.	Open a door by turning a door knob/ handle	_	 if no, why? (use code)
9.	Use a TV remote control		 if no, why? (use code)
	. Wash your hands (includes lathering and rit	_	 if no, why? (use code)

Codes for recording "no" responses:

- 1. "I used the unaffected arm entirely." (assign "0").
- 2. "Someone else did it for me." (assign "0").
- 3. "I never do that activity, with or without help from someone else because it is impossible." For example, combing hair for people who are bald. (assign "N/A" and drop from list of items).
- 4. "I sometimes do that activity, but did not have the opportunity since the last time I answered these questions." (carry-over last assigned number for that activity).
- 5. Non-dominant hand hemiparesis. (only applicable to #24; assign "N/A" and drop from list of items).

Amount Scale How Well Scale

11. Turning water on/off		if no, why? (use code)
with knob/lever on faucet		Comments
12. Dry your hands		if no, why? (use code)
13. Put on your socks		if no, why? (use code)
14. Take off your socks		if no, why? (use code)
15. Put on your shoes (includes tying shoestrings and fastening str	raps)	if no, why? (use code)
16. Take off your shoes (includes untying shoestrings and unfastening)	ng straps)	if no, why? (use code) Comments
17. Get up from a chair with armrests		if no, why? (use code) Comments
18. Pull chair away from table before sitting down		if no, why? (use code) Comments
19. Pull chair toward table after sitting down		if no, why? (use code)
20. Pick up a glass, bottle, drinking cup, or can (does not need to include drinking)		if no, why? (use code)

Codes for recording "no" responses:

- 1. "I used the unaffected arm entirely." (assign "0").
- 2. "Someone else did it for me." (assign "0").
- 3. "I never do that activity, with or without help from someone else because it is impossible." For example, combing hair for people who are bald. (assign "N/A" and drop from list of items).
- 4. "I sometimes do that activity, but did not have the opportunity since the last time I answered these questions." (carry-over last assigned number for that activity).
- 5. Non-dominant hand hemiparesis. (only applicable to #24; assign "N/A" and drop from list of items).

Amount Scale How Well Scale

Brush your teeth			if no, why? (use code)
(does not include prepara	ation of toothbrush		Comments
or brushing dentures unle	ess the dentures are br	ushed	
while left in the mouth)			
,			
22. Put on makeup base,			if no, why? (use code)
lotion, or shaving cream of	on face		Comments
,			
23. Use a key to			if no, why? (use code)
unlock a door			Comments
24. Write on paper			if no, why? (use code)
(If hand used to write pre	-stroke is more affecte	ed.	Comments
score item; if non-writing l			
drop item and assign N/A)		e ajjectea	,
an op trem and assign 1112)			
25. Carry an object in			if no, why? (use code)
your hand (draping an it	tem over the arm		Comments
is not acceptable)	iem over the arm		
is not acceptable)			
26. Use a fork or			if no, why? (use code)
spoon for eating (refers to	o the action		Comments
of bringing food to the mo			Comments
or spoon)	oun win jork		
27. Comb your hair			if no, why? (use code)
27. Como your nan			Comments
			Comments
28. Pick up a cup			if no why? (use code)
			if no, why? (use code)
by a handle			Comments
20 Button a chint			if no subset (see anda)
29. Button a shirt			if no, why? (use code)
			Comments
20 5 41 16 1 1 1			······································
30. Eat half a sandwich			if no, why? (use code)
or finger foods			Comments

Codes for recording "no" responses:

- 1. "I used the unaffected arm entirely." (assign "0").
- 2. "Someone else did it for me." (assign "0").
- 3. "I never do that activity, with or without help from someone else because it is impossible." For example, combing hair for people who are bald. (assign "N/A" and drop from list of items).
- 4. "I sometimes do that activity, but did not have the opportunity since the last time I answered these questions." (carry-over last assigned number for that activity).
- 5. Non-dominant hand hemiparesis. (only applicable to #24; assign "N/A" and drop from list of items).

Reasons for non-use

- 1 I used the unaffected arm entirely
- 2 Someone else did it for me
- 3 I never do that activity, with or without the help of someone else
- 4 I sometimes do that activity, but did not have the opportunity since the last time I answered these questions
- 5 Other

How Well Scale

0 – The weaker arm was not used at all for that activity

(never)

1 – The weaker arm was moved during that activity, but was not helpful

(very poor)

2 – The weaker arm was of some use during that activity, but needed some help from the stronger arm, moved very slowly, or with difficulty

(poor)

3 – The weaker arm was used for the purpose indicated, but the movements were slow or were made only with some effort

(fair)

4 – The movements made by the weaker arm were almost normal, but not quite as fast or accurate as normal

(almost normal)

5 – The ability to use the weaker arm for that activity was as well as before the stroke

(normal)

Treatment Received Form

Partici	pant ID:
	indicate the treatment you have received targeting your affected upper extremity enrolling in this research study (check all that apply):
	Inpatient Rehabilitation
	Outpatient Rehabilitation
	Botox
	Baclofen pump
	Other research studies
	Other:

Participant ID:
Date:
Testing Session:
Affected Hand (circle one): Right
Left

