- 2. Instruct them to wear the activity monitors on both arms for 2 days before treatment to establish a baseline of arm use.
- 3. Make sure participant knows to charge them overnight every night.
- 4. Instruct participant to watch CIMT videos on YouTube. Give them the link.

Treatment Day -1 (TD 1)

- 1. Turn video camera on & show participant ID, treatment day, date, and group
- 2. Complete Treatment Received Form
- 3. Introduce the **Treatment Contract** by reading/explaining each component of the therapy. Briefly present the research.
 - discuss the need for massed practice with the weaker arm and limited use of the stronger arm to drive brain plasticity.
 - discuss how quality of life improvements relate directly to the amount of use for daily activities, regardless of motor ability.
- 4. Home Achievement Record portion of Treatment Contract.
 - Compile list of daily activities done on both weekdays and weekends (one list)
 - Photocopy daily activities list prior to categorizing level of involvement of the weaker arm in each task (10 copies). Provide 1 copy to client to complete prior to next session.
 - Discuss involvement of the weaker arm in each task with problem-solving.
- 5. **Caregiver contract**. Provide instruction to family member/caregiver on problem-solving approach. ("You'll notice that I used a particular approach to help clients come up with solutions to some of the barriers to using the weaker arm.")
 - "Say" They come up with a plan. No questioning.
 - "Do" They try it out
 - "Check" To note what worked and what didn't. Revise the plan.
- 6. Ask participant if he/she watched the CIMT videos on YouTube. If they have not yet, assign as homework.
- 7. Ask participant about adverse events during previous session(s) and fill out **Adverse Event Reporting Form** if need be
- 8. Donn the mitt

- 9. Perform ~9 shaping tasks—document on **Task List**, **Shaping Data Sheets**, and **Shaping Graphs** (1 per task)
- Administer the full MAL-all 28 items using the How Well Scale only (add to MAL spreadsheet)
- 11. Turn video camera off and add comments to **Therapist Treatment Recording Log**
- 12. Store the video on the encrypted hard drive under the correct group and session subfolder

Treatment Day- 2 (TD 2)

- 1. Turn video camera on & say participant ID, treatment day, and group
- 2. Check the mitt time and record it on the Task List; donn the mitt. If mitt wear time is low, problem-solve compliance as needed.

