		 	 	 				 				
		-										
Mitt use tim	10											
(hours)	IC											
(hours)		 	 									
		•										

Shaping Data Sheet

				Snaping	Data	Sheet		
Task:				Pt Initial	s:		Subject ID:	
Date:			Trmt Day	/#:	Time:		Therapist:	
Shapi	ng Task D	escription	: Location spe	ecifics: Is the to	sk setup th	e same way?		
Place	the		:	(check one)		Place the _	:	(check one)
_	Center of	the patien	t				r of the patient	
_	To the rig	ht / left (circ	tle one) of the	patient		To th	e right / left (circle one) of t	he patient
_	Other					Other		
	inches	from the E	dge of Tal	ble		inc	hes from the Edge of T	able
	inches	from midli	ine			ine	hes from midline	
	other_					oth	er	
Heigh	it:	inches				Height:	inches	
	to Shape/M Paramete Paramete	Make the ta er 1Varied er 2Varied	(ParaV1) (ParaV2)	nallenging: :		4		_
rial	ParaM	ParaV1	ParaV2	ParaV3			Comments	
- 1461	Additi	raravi	Taravz	Taravs		op, recovery, or chniques that wo		

Trial	ParaM	ParaV1	ParaV2	ParaV3	Comments	
					-Note drop, recovery, or repositioning -Note techniques that work or don't work	
1						
2						
3						
4						
5					Avg (X)=	
6						
7						
8						
9						
10					Avg (X) =	

Video Recording Log

Treatment Day:	Comments about recording (i.e. session completely recorded, battery died, etc.)
1	
1	
2	
3	
4	
5	
6	
7	
8	
9	
10	
10	

Treatment materials – Gaming CI therapy Groups

Checklist Self-Gaming

Note: Bolded items are separate sheets within the treatment packet to be completed

Prior to Treatment (after pre-test)

- 1. Provide the activity monitors to participants and demonstrate use.
- 2. Instruct them to wear the activity monitors on both arms for 2 days before treatment to establish a baseline of arm use.
- 3. Make sure participant knows to charge them overnight every night.
- 4. Provide the smart watch to participants and demonstrate use (give them the **instructions** to take home with them).
- 5. Instruct them to wear the watch on the less affected arm for 2 days before treatment to establish a baseline of "normal" arm movement counts.
- 6. Have them record the values on the watch right before going to bed on the **Limb Activation Log**.
- 7. Instruct participant to watch CIMT videos on YouTube. Give him/her the link.

In-clinic Treatment Day 1 (2 hours)

- 1. Turn video camera on & say participant ID, treatment day, and group

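### Baseline accelerometry is recorded after allocation under conditions that differ by arm, so the baseline itself may differ by arm

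*Combined protocol and SAP*

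**What the plan says.** The Combined protocol and SAP gives each arm its own treatment checklist. Each opens with steps placed after the pre-test visit and before treatment. All four contain the same accelerometer step: "Instruct them to wear the activity monitors on both arms for 2 days before treatment to establish a baseline of arm use".

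Under Treatment materials – Gaming CI therapy Groups, the Self-Gaming and Tele-Gaming checklists both add the smart watch for those days: "Instruct them to wear the watch on the less affected arm for 2 days before treatment". The next step is "Have them record the values on the watch right before going to bed". The Pebble Watch Log agrees on placement, "The first two days (baseline days) you will wear the watch on your unaffected arm", and makes that count the later goal for the weaker arm. The Limb Activation Instructions ask for notifications to be on while the device is in use and describe a vibration after ten minutes without movement. They make no exception for the baseline days.

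Before treatment, the CI therapy checklist (Group 1) says "Instruct participant to watch CIMT videos on YouTube. Give them the link". Both gaming checklists say "Instruct participant to watch CIMT videos on YouTube. Give him/her the link". The Traditional Therapy Checklist (Group 4) stops after the monitor steps.

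The Data Analysis paragraph treats accelerometry and the Wolf Motor Function Test (WMFT) as primary, with the treatment-by-time interaction as the effect of interest. Measurement/Instrumentation lists accelerometers as secondary, and Aim 4a names the Motor Activity Log (MAL) and WMFT as primary.

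On later wear, the Limb Activation Instructions say "Wear the watch during all of your waking hours for the duration of your participation in the study". The gaming Treatment Contract sets a target of 10 hours a day on the weaker arm.

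**The concern.** Only participants allocated to gaming receive the watch, so allocation has been released before this baseline begins. By the document's own account the watch is treatment. The gaming checklists count it among four parts of the intervention, and the Group 2 description puts a biofeedback monitor in place of the mitt. The Background ties behaviour monitoring to behaviour change. One part of the intervention therefore runs during the baseline recording in two of the four arms.

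Randomisation protects a baseline only if it is measured before allocation can act on it. In a treatment-by-time model the baseline enters each arm's change, so a shift caused by allocation becomes part of the estimated effect. A larger sample does not shrink it. Adjusting for the measured baseline does not remove it either, because the measured value already carries the shift. The planned between-group comparison of initial scores cannot tell a chance difference from one caused by allocation, and could easily miss a modest one.

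The most exposed comparison is Group 2 with Group 4, which the Research Design section uses to judge whether gaming between sessions adds anything.

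**Working it through.** No figure in the plan can be reproduced here: the documents state no sample size, alpha, SD or effect size for this outcome. The check is a side-by-side reading, followed by two illustrations on stated assumptions.

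**1. Conditions between pre-test and treatment, from the four checklists**

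| Group | Monitors, both arms, 2 days | Watch on stronger arm, nightly log | Videos supplied |
|---|---|---|---|
| 1 Clinic CI therapy | yes | no | yes |
| 2 Self-gaming | yes | yes | yes |
| 3 Tele-gaming | yes | yes | yes |
| 4 Standard therapy | yes | no | no |

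**2. Which contrasts are exposed**

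Let s be the mean shift in an arm's baseline caused by these conditions, w the part due to the watch and v the part due to the videos, taken as additive and with v equal wherever videos are supplied. Then s1 = v, s2 = s3 = w + v and s4 = 0. If later recordings are unaffected, the estimated difference in change between arms A and B equals the true difference minus (sA − sB).

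- Group 2 minus Group 4: bias −(w + v).
- Group 1 minus Group 2 or 3: bias +w.
- Group 2 minus Group 3: bias 0.

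The MAL and WMFT pre-test scores precede these steps, so this route does not reach them.

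**3. Direction**

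The documents do not define the accelerometry summary. Suppose it is a weaker-to-stronger ratio with an assumed starting value of 0.50. If stronger-arm movement rises by a fraction p and weaker-arm movement by q, the ratio becomes 0.50 × (1 + q)/(1 + p).

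- q = 0 and p = 5%, 10%, 20%: shifts of −0.024, −0.045, −0.083.
- p = 0 and q = 10%: 0.55, a shift of +0.050.
- p = q: no shift.

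If the summary is instead a weaker-arm count, p does not enter it directly. The sign therefore depends on an undefined endpoint and on two unmeasured reactions.

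**4. What a shift would do to a test**

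Assume a two-arm change contrast, no true effect, two-sided alpha 0.05 and a shift of d SDs of change in one arm only. With se = √(2/n), the false-positive rate is Φ(d/se − 1.96) + Φ(−d/se − 1.96).

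For n = 20 and d = 0.2: se = 0.316 and d/se = 0.632, so the rate is Φ(−1.328) + Φ(−2.592) = 0.092 + 0.005 = 0.097.

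| Assumed n per arm | d = 0.1 | 0.2 | 0.3 | 0.5 |
|---|---|---|---|---|
| 20 | 6.2% | 9.7% | 15.8% | 35.3% |
| 30 | 6.7% | 12.1% | 21.3% | 49.1% |
| 40 | 7.3% | 14.5% | 26.9% | 60.9% |
| 60 | 8.5% | 19.5% | 37.6% | 78.2% |

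At d = 0 the rate is 5%. Nothing in the documents says which column, if any, applies.

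**The case against.** The strongest reply is that the checklists show different exposure, not a different baseline. The watch is on the stronger arm for a reason: its count supplies the goal for the weaker arm. A participant may also choose to display the count, in which case the vibration does not work. Three stronger readings are tempting, and the documents support none of them.

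- A reader might infer that a primary outcome's baseline has been altered. Accelerometry is primary only in the Data Analysis paragraph; Measurement/Instrumentation and Aim 4a say otherwise. No passage reports that wearing the watch changed arm use.
- A reader might infer that the gaming arms' baseline falls by 0.024 to 0.083 and reappears as false gain over Group 4. Those figures need a ratio endpoint that is nowhere defined, and they ignore any opposite effect of the videos, which the same arms receive. Viewing within the two days is not fixed either: videos not yet watched become homework from Treatment Day 1.
- A reader might infer that watch feedback contaminates the post-treatment and 6-month recordings. That rests on one literal instruction. The log ties the goal to the intervention period, the gaming follow-up steps mention only the MAL, and the checklists do not say when monitors are worn after treatment.

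All of this limits the claim. What remains is that the conditions differ by arm, that they do so after allocation, and that this baseline feeds the analysed effect. The watch argument does not depend on when the videos are seen. A visible count logged each night is still feedback, with or without vibration.

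**Conclusion.** The concern holds as a risk of bias that the schedule creates and could avoid. Baseline accelerometry may differ by arm because of allocation. If it does, the contrasts of Group 2 with Group 4 and of Group 1 with Groups 2 and 3 are biased by the difference in shift, and the planned analysis cannot remove it. Group 2 with Group 3 is spared, provided both react alike to identical steps.

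Size and direction cannot be determined from the documents; both illustrations above rest on assumed inputs. The weight of the point depends on whether accelerometry is primary, which the document must settle, but the flaw remains if it is secondary. It merits correction because the remedy is cheap.

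**What to change.** - In all four arms, complete the two-day accelerometer recording before the watch and videos are handed over, and ideally before allocation is disclosed to participants and treating staff.
- Obtain the watch's stronger-arm reference count afterwards, as a separate step in Groups 2 and 3. Using the bilateral monitors for that goal would need evidence, absent here, that their counts match the watch app's and reach therapists in time.
- Define the accelerometry summary and state once whether it is primary or secondary.
- Reconcile the watch-wear statements in the gaming Treatment Contract, the Limb Activation Instructions and the Pebble Watch Log. State whether the watch is worn during the post-treatment and 6-month recordings, so that those are made under the same conditions in all arms.

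The cost is up to about two more days, or one more hand-over, before treatment. Two days of monitors followed by two of watch reference make 2 + 2 = 4 days, which fits the one-week pre-treatment window. Withholding allocation until the recording ends also means changing when it is released, which is more than a reordering of checklist lines.
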